9.1 Study design

This is a population-based retrospective cohort study with a nested case-control analysis to assess safety and effectiveness of new users of rivaroxaban and apixaban versus new users of warfarin in a cohort of NVAF patients from THIN database (secondary data) in the UK.

All patients aged 18 and above and who have been enrolled in the databases for at least 1 year and had their first prescription recorded in the databases at least 1 year ago will be included in source population. A patient will be considered eligible to enter a study cohort as a new-user of one of the three study drugs when he or she has a first prescription of the index drug recorded during the enrollment period. Individuals meeting the criteria of new user of more than one study drug during the enrollment period will be assigned to the study cohort with the earliest start date. Among the three study cohorts, we will further identify patients with Non-valvular Atrial Fibrillation (NVAF) defined as: Patients with a record of Atrial fibrillation (AF) any time prior start date or within the 2 weeks after the start date, and free of valvular replacement or mitral stenosis prior to start date or 2 weeks after start date.

Additionally, NVAF patients with other recent indications of OAC initiation will be excluded. Thus patients with an entry of venous thromboembolism or orthopedic arthroplasty recorded in the last 3 months before the date of first time use of OAC or in the week after the start date will be excluded from the study cohort. Individuals on more than one OAC on the start date will also be excluded.

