Once all these steps are applied, then daily dose will be derived as the simple product of posology value and strength of the selected prescription. Once the daily dose is computed for all NOACs following the rules described above, we will change the daily dose of rivaroxaban assigned to 40 mg to 20 mg when the posology derived from dividing the quantity (number of tablets) by days of time interval between consecutive prescriptions (gap between prescriptions less than 90 days) results in 20 mg daily dose: consequently, correcting the information indentified from the instructions field of the database in this scenario. This amendment to the algorithm was introduced as a result of our exercise in Study 19330, unpublished data. In the case of rivaroxaban, we found that estimating daily dose based on dose instructions (those recorded in the free text field) sometimes results in misclassifying as 40mg daily dose, usage that should be classified as 20mg daily dose according to pill count.

Furthermore estimated daily doses for both start date and index date, will be classified according to whether or not estimated daily dose corresponded to a standard dose. When estimated daily dose at index date, only prior prescriptions will be taken into account. For rivaroxaban a daily dose of 20mg will be considered as “standard dose”. Daily doses of 15mg will be considered a “reduced dose”. For apixaban a daily dose of 10mg will be considered as “standard dose”. Daily doses of 5mg will be considered as “reduced dose”.

For warfarin we will also obtain posology from free text recorded instructions for the prescription using the following criteria:

- 1.- When instructions assign 1, 2 or 3 per day we will consider them as valid and apply that posology.
- 2.- If instructions are missing, not mapped to a value, or mapped to posology other than 1,2, 3 per day, we will assign a value of 1 per day.

Warfarin daily dose will be derived as the simple product of posology value and strength of the selected prescription. In the case of more than one prescription of warfarin on same day (usually different strengths) the daily dose will be the sum of daily doses of all different prescriptions recorded on that day, and the length of supply the largest supply among all different prescriptions recorded on that day.

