9.3.1.2 Dose Reduction Criterion

- **Apixaban:**

- The recommended dose of apixaban is 2.5 mg taken orally twice daily in patients with NVAF and at least two of the following characteristics: age \geq 80 years, body weight \leq 60 kg, or serum creatinine \geq 1.5 mg/dL (133 micromole/L).
- NVAF patients with severe renal impairment (creatinine clearance 15-29 mL/min) patients should receive the lower dose of apixaban 2.5 mg twice daily for the prevention of stroke and systemic embolism.

- **Rivaroxaban:**

- In patients with moderate (creatinine clearance 30 - 49 ml/min) or severe (creatinine clearance 15 - 29 ml/min) renal impairment, the recommended dose is 15 mg once daily for the prevention of stroke and systemic embolism in patients with non-valvular atrial fibrillation.

- **Warfarin:**

- Warfarin itself does not have dose-reduction requirements however the dose needs to be titrated to maintain INR between 2.0-3.0. In this study, we would not use the dose adjusting criterion for warfarin as it is variable and difficult to take in to account.

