- Healthcare utilization in the year prior to the start date/index date (e.g. GP visits, outpatient visits and hospital admissions where available).
- Use of following medications in the three months before the start date: antiplatelet drugs (low-dose acetylsalicylic acid, clopidogrel, dipyridamole, prasugrel, ticlopidine and ticagrelor), antiarrhythmic drugs, antihypertensive drugs, statins, anti-diabetic agents, non-steroidal anti-inflammatory drugs, oral steroids, acid-suppressive drugs, disease-modifying anti-rheumatic drugs, antidepressants, antipsychotic drugs, oral contraceptives, hormone-replacement therapy, strong inhibitors of either cytochrome P450 3A4 or P-glycoprotein (e.g. the systemic azole antimycotics ketoconazole, itraconazole, voriconazole and posaconazole and the HIV-protease inhibitor ritonavir), strong CYP3A4 inducers (e.g. rifampicin, phenytoin, carbamazepine or phenobarbital) and fluconazole.
- Recency of use of medications listed above as well as study drugs on index date will be categorized as:
 - Current use (when the drug supply lasts until index date or supply ends in the 30 days before index date)
 - Recent use (when the drug supply ends 30-90 days before index date)
 - Past use (when the drug supply ends 91-365 days before index date)
 - Non-use: no use in year before index date

Note that for medications other than study drugs, recent and past will be collapsed into one category

- Duration of use will be defined among current users of study drugs at index date as the time from the first consecutive prescription of that drug to index date. Consecutive prescriptions will be considered those separated by a gap of less than 30 days between end of supply and the date of the next prescription. Duration of use will be classified as: up to 90 days, 91 days up to one year, 1-3 years, more than 3 years. Furthermore, these individuals (i.e. current users of study drugs at index date) will be classified as “Continuers” if the first consecutive prescription corresponds to the patient’s start date (i.e. the patient maintained the same drug initiated at start date up until the index date), or “Discontinuers/Switchers” if the patient was not continuously taking the starting OAC between start and index date (i.e. either the patient has interrupted the drug at some point or the patient switched from one OAC to another).

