renal function values available (expected to be less than 5%) will be excluded from these analyses. Using warfarin current use as the reference category, we will estimate the risk of the study outcomes associated to the rivaroxaban and apixaban daily dose categories described above.

- c) OAC duration: We will use the duration variable described in section 9.3.3. to compare different drug durations of current use with non-use of each study drug. Additionally we will compare “Continuers” and “Discontinuers/Switchers” with non-use of each study drug.
- d) Stratified analysis: The above described analyses will also be conducted separately for naïve, and non-naïve patients at start date.

Comparisons will be done based on adjusted point estimates and confidence intervals obtained from multivariable regression.

We will describe the patterns of use of study medication or other NOACs (edoxaban/dabigatran) after intracranial hemorrhage events, and ischemic events that occurred during the study period. The current hypothesis is that a patient will restart with anticoagulation within 1-3 months of an event.

Strategy for handling missing data

As a general strategy, no data imputation strategies will be applied to supplement missing data. However, missing values may occur in a small proportion. In this case, individuals with missing values will be kept in the analysis and a separate category will be created for missing values of that variable.

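### As written, the warfarin posology fallback and drug-by-drug current use can misplace patients in or out of the warfarin reference group

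*Protocol*

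**What the plan says.** Section 9.3.1.1 takes warfarin tablets per day from the free-text instructions: "When instructions assign 1, 2 or 3 per day we will consider them as valid and apply that posology". Instructions that are absent or cannot be mapped get 1 per day, and so do those that are "mapped to posology other than 1,2, 3 per day, we will assign a value of 1 per day". When several warfarin prescriptions fall on one day, daily doses are summed and "the length of supply the largest supply among all different prescriptions recorded on that day" is used.

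Section 9.3.3 then sets exposure at the index date: "Current use (when the drug supply lasts until index date or supply ends in the 30 days before index date"). The definition is applied to each drug on its own. Nothing in it ends the supply of one OAC when a different OAC is prescribed.

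Section 9.7 lists the rivaroxaban and apixaban dose contrasts, each against warfarin, and fixes the comparator: "Using warfarin current use as the reference category". Concurrent OAC use is addressed only at cohort entry (Section 9.1): "Individuals on more than one OAC on the start date will also be excluded".

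**The concern.** Current use depends on when supply runs out, and supply length depends on tablets per day. The fallback therefore helps decide who belongs to the warfarin reference. The NOAC fallbacks (apixaban twice daily, rivaroxaban once daily) match the regimens named in the objectives. Warfarin has no fixed tablet count: Section 9.3.1.2 says that "the dose needs to be titrated to maintain INR between 2.0-3.0". A single default is least suited to this drug, and the rule discards values that were successfully read.

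Two errors would follow. Supply that is too long keeps patients who have stopped in the reference; supply that is too short removes true users or breaks their continuous use. Separately, a patient who has just switched can satisfy the definition for two drugs at once, one of them the reference and the other the drug under test. The primary dose contrasts would then rest partly on a coding convention.

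**Working it through.** **The plan's own figures.** The protocol gives no figure for misclassification of the reference. The nearest is in Section 9.5: detectable ORs of 2.3 / 1.8 / 1.6 (ICH / ischaemic stroke / death) for inappropriate reduced-dose apixaban against current warfarin.
- Events: 30,000 x 1% / 2% / 4% x 3 years = 900 / 1,800 / 3,600, as stated. The 3 years is not stated; it is the value that reproduces the figures.
- Current warfarin holds 1/3 x 50% = 1/6 of events, and the apixaban category is 15% as large. Cases = events/6 x 1.15 = 172.5 / 345 / 690. Exposure among controls = 0.15/1.15 = 0.130.
- With one control per case (assumed) and two-sided 5%, power is 84.5% / 81.8% / 89.0%. The stated figures hold. They make no allowance for misclassified reference time.

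**Step 1: supply.** Supply = quantity / tablets per day (implied, not written out for warfarin). Current use runs to supply + 30 days. Pack sizes and true tablet counts are assumptions.

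| Tablets | True per day | Assigned per day | Current until, as written | Current until, true posology | Error |
|---|---|---|---|---|---|
| 56 | 4 (readable) | 1 | 56 + 30 = day 86 | 14 + 30 = day 44 | 42 days too long |
| 84 | 5 (readable) | 1 | 84 + 30 = day 114 | 16.8 + 30 = day 46.8 | 67.2 days too long |
| 56 | 0.5 (readable) | 1 | day 86 | 112 + 30 = day 142 | 56 days too short |
| 56 | 2 (text missing) | 1 | day 86 | 28 + 30 = day 58 | 28 days too long |
| 56 | 1 (text missing) | 1 | day 86 | day 86 | none |

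Over-long supply matters only after the last prescription, because a patient who keeps refilling is current anyway. Over-short supply also matters between refills. A half-tablet user refilling 56 tablets every 112 days shows a gap of 112 - 56 = 56 days. Section 9.3.3 requires gaps under 30 days, so this continuous user is classed as a Discontinuer.

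**Step 2: switch.** Suppose warfarin supply runs out on the day apixaban is first prescribed, 20 days before the index date. Warfarin supply ended 20 days earlier, which is within 30, so the patient is a current warfarin user. Apixaban supply covers the index date, so the patient is also a current apixaban user. The start-date exclusion and start-date cohort assignment do not reach the index date. The Discontinuers/Switchers label is compared with non-use in item (c) of Section 9.7 and does not restrict the warfarin reference.

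**Step 3: possible effect.** Let f be the share of current-warfarin time that is really off drug, and k the outcome rate off drug relative to on warfarin. Then observed OR = true OR / (1 - f + f x k). Neither f nor k is in the protocol.
- Stroke, k = 2.0, true OR 1.0: 1/1.05 = 0.95, 1/1.10 = 0.91, 1/1.20 = 0.83 at f = 5 / 10 / 20%.
- ICH, k = 0.5, true OR 1.0: 1/0.975 = 1.03, 1/0.95 = 1.05, 1/0.90 = 1.11.
- At Section 9.5's detectable stroke OR, k = 2.0: 1.8/1.05 = 1.71, 1.8/1.10 = 1.64, 1.8/1.20 = 1.50.

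To place f: if off-drug time equals on-drug time, as with the 50% planning assumption, and a share m of it is misread as current, f = m/(1 + m). Reaching f = 20% needs m = 25% (0.25/1.25).

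These values of k do not apply to switched patients, who are taking a NOAC. If they sit in the reference while on the tested NOAC, k is the true OR itself. A true 1.0 is then unmoved, and a true 1.8 at f = 10% reads 1.8/(0.9 + 0.18) = 1.67. Off-drug and switched time therefore act differently.

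**The case against.** The strongest reply is that this is a fallback and a silence, not a general fault.

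- **Scope.** A reader might infer that warfarin supply generally rests on one tablet per day, or that every contrast is affected. Neither follows. Instructions of 1, 2 or 3 are applied as read, and the duration and Continuer comparisons in item (c) of Section 9.7 use non-use as reference.
- **Asymmetry.** A reader might infer that the error is confined to warfarin. It is not. The 30-day window and the missing cut at a switch apply to all study drugs, and the NOACs have fallbacks of their own. Only the 1-per-day fallback is specific to warfarin.
- **Pill count.** A reader might say that warfarin is denied a check the protocol gives to NOACs. The check is narrow: "we will change the daily dose of rivaroxaban assigned to 40 mg to 20 mg". It corrects one known dose error, is not a supply rule, and does not cover apixaban.
- **Other safeguards.** Section 9.1 mentions manual fine tuning from recent prescription history, but it is written about daily dose and sets no rule for warfarin supply or overlapping OACs. Section 9.7 adjusts for OAC use at the index date without saying how a patient current on two drugs is coded.
- **SAP.** An analysis plan that is not shown may rank overlapping exposures. The silence alone would be a weak point. But current use is already defined in the protocol, and that definition admits both drugs at once.

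All the limits on scope, asymmetry and pill count stand. None removes the overwriting of readable values or the double classification.

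**Conclusion.** The point holds in limited form. Followed literally, the text discards readable warfarin posologies and lets one patient be current on the reference and the tested drug together. Both affect the group behind the primary dose contrasts, and nothing else in the protocol resolves them.

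It would go too far to say that the reference is shown to contain a material share of off-drug or switched patients. The protocol gives no frequency of defaulted posology, no pack sizes and no switching rate. Over-long and over-short supply work in different ways, and off-drug and switched time need not bias in the same direction. The ORs of 0.95-0.83 and 1.03-1.11 show what 5-20% off-drug time could do under the assumed rate ratios; they are not estimates for this study. The size and net direction of bias are unknown. The change is still worth making before analysis, because it is cheap.

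**What to change.** 1. In Section 9.3.1.1, apply any plausible mapped warfarin posology instead of replacing values other than 1, 2 or 3 with 1.
2. In Section 9.3.3, for exposure classification, end the supply of one OAC on the date a different OAC is prescribed, and classify by the most recently prescribed OAC at the index date. Current-use categories then become mutually exclusive for all study drugs.
3. Where posology is missing or unmapped, keep the 1-per-day default in the main analysis. Add a sensitivity analysis with supply derived from the patient's own earlier quantities and prescription intervals, or with a varied grace window. Report how often the default was used.

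The cost is a few sentences and some programming on fields already extracted. Interval-derived supply can read a real interruption as slower use and so hide true gaps, which is why it belongs in a sensitivity analysis only. A first prescription has no earlier interval and still needs the default.

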9.3.1.2 Dose Reduction Criterion

- **Apixaban:**

- The recommended dose of apixaban is 2.5 mg taken orally twice daily in patients with NVAF and at least two of the following characteristics: age \geq 80 years, body weight \leq 60 kg, or serum creatinine \geq 1.5 mg/dL (133 micromole/L).
- NVAF patients with severe renal impairment (creatinine clearance 15-29 mL/min) patients should receive the lower dose of apixaban 2.5 mg twice daily for the prevention of stroke and systemic embolism.

- **Rivaroxaban:**

- In patients with moderate (creatinine clearance 30 - 49 ml/min) or severe (creatinine clearance 15 - 29 ml/min) renal impairment, the recommended dose is 15 mg once daily for the prevention of stroke and systemic embolism in patients with non-valvular atrial fibrillation.

- **Warfarin:**

- Warfarin itself does not have dose-reduction requirements however the dose needs to be titrated to maintain INR between 2.0-3.0. In this study, we would not use the dose adjusting criterion for warfarin as it is variable and difficult to take in to account.

9.3.2 Outcomes definition

The outcomes include

- Intracranial hemorrhage (intracerebral hemorrhage, subarachnoid hemorrhage, subdural and epidural hematoma)
- Ischemic event (Ischaemic Stroke /Systemic Embolism),
- Myocardial Infarction
- All cause-mortality

See section [Annex 3: Additional information](#) for corresponding codes.

9.3.2.1 Validation of outcomes

Anonymized free text will be obtained for all individuals experiencing safety or effectiveness events (as defined above) during the study period. We will manually review their clinical profiles with available free text to confirm or discard these events. Since the study cohort will include individuals with a history of ischemic and/or hemorrhagic events before the study period, this manual review of clinical profiles would be essential to discard diagnosis recorded during the study period that actually refer to episodes that occurred before start date. Furthermore, only events that required

hospitalization will be considered. For this process of validation of the outcomes, all patient personal identifiers will be suppressed and information on drug use removed to allow for a blinded revision of patient profiles. Additionally we will obtain anonymized free text from a random sample of individuals (n=100) that allegedly do not experience safety or effectiveness events (i.e. no event codes recorded). We will manually review their clinical profiles with available free text to identify any signs of safety or effectiveness events (meeting our operational definition) that had not been identified through the code search.

9.3.3 Covariate definition

The following variables will be collected among the three study cohorts (apixaban, rivaroxaban and warfarin) both at start and index date (the date among cases and controls):

- Age and sex distribution at start date/index date
- Naïve/Non-Naïve at index date: Use of OAC other than the index OAC before index date
- Frailty: we will estimate an electronic frailty index (eFI) at start date/index date by using an algorithm developed and validated in THIN (Clegg et al. 2016). Briefly the eFI score is simply an equally weighted calculation of deficits present out of the total 36 deficits identified. Patients will be classified into four mutually exclusive categories based on this score: a) Fit = 0-0.12, b) Mild frailty = 0.12-0.24, c) Moderate frailty = 0.24-0.36, and d) Severe frailty = >0.36.
- Renal disease: estimated glomerular filtration rate (eGFR) before start date/index date will be calculated using the formula described in Table S1 (Annex 3). In prior studies we found that eGFR could not be estimated in less than 5% of AF patients. ACR (Albumin/Creatinine Ratio) will also be ascertained.
- Comorbidity: history of haemorrhagic disease and history of intracranial haemorrhage, urogenital bleeding and gastrointestinal bleeding. Liver disease, pancreatic disease, cancer, cardiovascular disease (acute MI, coronary artery disease, congestive heart failure, ventricular arrhythmia, peripheral arterial disease) cardiovascular risk factors (hypertension, diabetes mellitus, hyperlipidaemia and obesity), stroke/TIA, respiratory disease (asthma and chronic obstructive pulmonary disease), rheumatoid arthritis, osteoarthritis, gastrointestinal disease, liver disease and pancreatic, alcohol-related disorders before start date/index date.
- CHADS2 (0-6) and CHA₂DS₂Vasc (0-9) scores will be calculated at start and index date based on the presence/ history of congestive heart failure, hypertension, age, diabetes mellitus and prior stroke or transient ischaemic attack. HAS-BLED (0-9) score for major bleeding risk (hypertension, renal disease, liver disease, stroke history, prior major bleeding or predisposition to bleeding, age > 65, medication usage predisposing to bleeding, alcohol usage history), will also be calculated. Numbers and proportion will be calculated per value.
- Smoking status, body mass index (BMI) and Townsend score: most recently recorded value before the start date/index date.

- Healthcare utilization in the year prior to the start date/index date (e.g. GP visits, outpatient visits and hospital admissions where available).
- Use of following medications in the three months before the start date: antiplatelet drugs (low-dose acetylsalicylic acid, clopidogrel, dipyridamole, prasugrel, ticlopidine and ticagrelor), antiarrhythmic drugs, antihypertensive drugs, statins, anti-diabetic agents, non-steroidal anti-inflammatory drugs, oral steroids, acid-suppressive drugs, disease-modifying anti-rheumatic drugs, antidepressants, antipsychotic drugs, oral contraceptives, hormone-replacement therapy, strong inhibitors of either cytochrome P450 3A4 or P-glycoprotein (e.g. the systemic azole antimycotics ketoconazole, itraconazole, voriconazole and posaconazole and the HIV-protease inhibitor ritonavir), strong CYP3A4 inducers (e.g. rifampicin, phenytoin, carbamazepine or phenobarbital) and fluconazole.
- Recency of use of medications listed above as well as study drugs on index date will be categorized as:
 - Current use (when the drug supply lasts until index date or supply ends in the 30 days before index date)
 - Recent use (when the drug supply ends 30-90 days before index date)
 - Past use (when the drug supply ends 91-365 days before index date)
 - Non-use: no use in year before index date

Note that for medications other than study drugs, recent and past will be collapsed into one category

- Duration of use will be defined among current users of study drugs at index date as the time from the first consecutive prescription of that drug to index date. Consecutive prescriptions will be considered those separated by a gap of less than 30 days between end of supply and the date of the next prescription. Duration of use will be classified as: up to 90 days, 91 days up to one year, 1-3 years, more than 3 years. Furthermore, these individuals (i.e. current users of study drugs at index date) will be classified as “Continuers” if the first consecutive prescription corresponds to the patient’s start date (i.e. the patient maintained the same drug initiated at start date up until the index date), or “Discontinuers/Switchers” if the patient was not continuously taking the starting OAC between start and index date (i.e. either the patient has interrupted the drug at some point or the patient switched from one OAC to another).

